3. STUDY OBJECTIVES

3.1 Primary Objective

Phase 1 To explore the characteristics, patterns and outcomes of patients (up to 30 years of age) that present with signs and symptoms of head injuries to one major tertiary referral hospital ED over a 36 months. To establish the number of patients (up to 30 years of age) who are discharged from ED or admitted to the ward with the diagnosis of head injury.

Phase 2 To follow up on the patient's journey at 10-14 days and four weeks from discharge.

Secondary Objectives

- 1) To determine current ED management and discharge processes for patients with a head injury and discharged home or admitted to the ward.
- 2) How are head injury patients managed in the community and the need for further management.

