4.4 Study sites

Royal North Shore Hospital Emergency Department

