4.6 Primary and Secondary Outcome Measures

Primary outcome:

- To explore the characteristics, patterns and outcomes of patients that present with head injuries to one major tertiary referral hospital ED.
- How are head injury patients managed in the community and the need for further management.

Secondary outcomes:

- To compare data both pre and during the COVID-19 pandemic
- Identification of evidence based concussion assessment and management in the ED
- How were head injury patients managed in the ED
- Identification of the type and appropriateness of discharge information, education and instructions
- What discharge instructions were provided for commencing post head injury activities such as return to school, work and sporting activities
- What were the patterns of community referrals

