5. PARTICIPANT ENROLLMENT AND RANDOMISATION

5.1 Recruitment

Patients up to the 30 years of age have been included in the study as this patient cohort are more likely to be involved in team contact sports and less likely to have co-morbidities. Posters will be positioned in all areas of the ED (with the exception of the resuscitation bays).

Phase 1: A 36 month (1st January 2019 - 31st December 2021) eMR audit of all patients (up to 30 years of age) presenting to ED will be reviewed for evidence of head injuries. Limitation of snowmed diagnostic codes will require review of all emergency presentations eMR to determine patients that have presented or been discharged with signs/symptoms of head injury or concussion. Review of eMR will be undertaken by the lead researcher to identify participants meeting inclusion criteria for phase 1. Due to the large number of patient records being accessed data for 2021 will only be accessed in early 2022 and as such, will be retrospective in nature.

Phase 2: A 12 month (1st January – December 31st 2021) prospective study of patients (up to 30 years of age) who present to ED with a head injury will be included in the study. The aim of the telephone interview is to collect data after the patient has been discharged from the ED. To obtain information from the patient such as; feedback on the discharge process, ongoing symptoms, return to sport, school, study or work or the need for further medical review.

For phase 2 potential participants will identified then recruited by clinicians or the emergency research volunteers, who will seek written consent whilst they are in the ED to participant in two telephone interviews.

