All patients will have the opportunity to opt out of the study without any impact on care practices. Randomisation will occur 1:1 ratio for patients < 16 years of age and patients > 16 years of age to identify 20 participants per week, who will be contacted 10-14 days post injury and then four weeks post discharge. Telephone interviews will be conducted by either ED research volunteers, the lead researcher or associate researchers from the RNSH ED Office. Prior to the commencement of the telephone interview each patient/parent/carer on contact will be again given the opportunity to opt out and verbal consent will be obtained. Each participant will be invited to select an interview schedule time suitable for them. Potential participants will only be contacted three times and if unable to be contacted will be considered as declining to participate in the study. Potential participants will only be contacted between the hours of 0800am until 0600pm (Monday – Friday).

All emergency clinicians will be briefed about the study via email, posters and short in-services.

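### Phase 2 runs in the same ED in 2021, half of the audit's 2020-21 period, so any effect it has on recorded management, discharge advice or referral could not be told apart from a pandemic effect

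*Protocol*

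**What the plan says.** Protocol 4.4 names one site for both phases, "Royal North Shore Hospital Emergency Department". Section 5.1 sets the Phase 1 window as "A 36 month (1st January 2019 - 31st December 2021) eMR audit of all patients (up to 30 years of age") and the Phase 2 window as "A 12 month (1st January – December 31st 2021) prospective study of patients (up to 30 years of age"). The same section says that "Posters will be positioned in all areas of the ED (with the exception of the resuscitation bays") and that "All emergency clinicians will be briefed about the study via email, posters and short in-services". Clinicians or research volunteers find eligible patients and seek consent while the patient is still in the department.

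Section 4.6 lists as a secondary outcome "To compare data both pre and during the COVID-19 pandemic", and the secondary objectives under 3.1 include "To determine current ED management and discharge processes for patients with a head injury". Section 8 takes the audit data from what ED staff write: assessment and diagnostic code, discharge summary, nursing notes and community referrals, among others.

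Section 5.1 calls the 2021 audit data retrospective because they will not be opened until early 2022. The protocol gives no calendar date at which the pandemic period begins, no date for the first briefing or poster, and no comment on the overlap of the two phases.

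**The concern.** Phase 2 concerns head injury and the discharge process. Phase 1 measures ED management, discharge instructions and referral for head injury in the same department. Clinicians who know that the topic is under study, and who are asked to identify patients for it, may document more fully, give more advice or refer more often. No part of 2019 carries this exposure, and 2021 does. A before/during comparison that includes 2021 would therefore attribute any such change to the pandemic.

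The description of current ED practice is affected in the same way. Part of it would come from a year in which staff knew that the subject was being studied. Section 11 expects the findings to change discharge policy, so a baseline that looks better than unobserved practice could understate the gaps.

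Opening the 2021 records later does not remove the problem. The care was given and written up while Phase 2 was recruiting.

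**Working it through.** **The plan's own figures.** 89,000 presentations a year × 3 = 267,000, as in 4.3 and 8.1. 5% × 89,000 = 4,450 head injuries, which is a one-year figure. Both reproduce. The point rests on the dates, and these counts serve only the illustration below.

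**Overlap in time.** Audit: January 2019 to December 2021, 36 months. Phase 2 recruitment: January to December 2021, 12 months.
- If the pandemic side is 2020-21: 12/24 = 50% of its months overlap with Phase 2.
- If it starts in March 2020 (assumption, as the protocol gives no date): 12/22 = 54.5%.
- Pre-pandemic months that overlap: none in either case.

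**What a study effect would do.** Suppose that Phase 2 raises a recorded item by x percentage points in 2021 and that the pandemic itself has no effect. With equal monthly case numbers (assumption), the apparent before/during difference is x × share, that is 0.50x to 0.55x.

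**Illustration of scale.** The values of x are assumed, since the documents give none. Take a baseline of 50% (assumption), a share of 0.50 and a two-sided 5% test. The apparent difference is d = 0.50x. Its standard error is √[p₁(1−p₁)/n₁ + p₂(1−p₂)/n₂], with p₁ = 0.50, p₂ = 0.50 + d and n₂ = 2n₁. The chance of p < 0.05 is Φ(d/SE − 1.96). Two case numbers are shown: 4,450 v 8,900 on the protocol's annual figure, and 1,335 v 2,670 if only 30% of those cases are aged up to 30 (assumption).

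| Assumed 2021 effect | Apparent difference | Chance of p < 0.05, 4,450 v 8,900 | Chance of p < 0.05, 1,335 v 2,670 |
|---|---|---|---|
| 2 points | 1.0 point | 19% | 9% |
| 5 points | 2.5 points | 78% | 32% |
| 10 points | 5.0 points | over 99% | 85% |

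Worked line for 5 points and the larger numbers: SE = √(0.25/4,450 + 0.249375/8,900) = 0.00918; 0.025/0.00918 = 2.72; Φ(2.72 − 1.96) = 78%.

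**Does the plan separate 2021?** Section 8 names the t test and chi-square for comparisons. Section 1.3 also mentions ANOVA and Kruskal-Wallis, which could compare three years, but does not assign them to calendar years. Section 8.2 speaks only of frequencies, central tendency and incomplete data. None of these treats 2021 differently from 2020.

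**Which outcomes are exposed.** Under 5.1, the lead researcher reviews all presentations for signs of head injury because diagnostic codes are unreliable. Case finding for Phase 1 therefore does not depend on the Phase 2 list or on the code that a briefed clinician chose. Assessment, advice and referral have no such independent check: the audit can see only what was written down.

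**The case against.** The case against has real force on several points.

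- **No effect is shown.** The briefings are about the study, and the protocol describes no training in assessment, documentation or referral. The posters are recruitment notices. A reader might infer that study effects are already being counted as pandemic effects. The documents support only the conditional: if there is an effect, it cannot be separated. The exposure throughout 2021 is itself inferred from the recruitment window. The study opens in November 2020 (4.5), so briefings could have begun slightly earlier.
- **The presentation rate is little affected.** A reader might also infer that a true pandemic fall in presentations would be masked. Notices inside an ED are not a plausible cause of arrivals, and the review of all presentations limits the influence of labelling. That reading is not supported.
- **Pooling is not fixed.** The synopsis lists the three years, no pandemic cut date is set, and the tests in 1.3 allow more than two groups. Reporting by year is compatible with the text, and an analysis plan not shown here could define the periods. This stands as a reason for modest wording. It does not remove the overlap, which is a design feature of the protocol.
- **Dropping 2021 from the main comparison would cost too much.** It would halve the 2020-21 period from 24 months to 12 and take the most recent year out of the account of current practice. This also stands, so 2019 v 2020 belongs in a sensitivity analysis and should not replace the main comparison.

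What remains is that the exposed items come from the same staff in the same year, and the text provides no way to tell the two explanations apart.

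**Conclusion.** The concern holds in a limited form. Any influence of Phase 2 on recorded assessment, discharge advice or community referral would fall only on the pandemic side of the Phase 1 comparison and would be indistinguishable from a pandemic effect. About half of it (50%, or 54.5% with a March 2020 start) would appear in a pooled 2020-21 figure, given roughly equal monthly case numbers. The size of the influence is unknown and may be nil. The percentages in the table show only that an effect of a few points could matter at these sample sizes.

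The count of presentations is much less exposed and is not part of the conclusion. The study is descriptive and unpowered, so this is an inexpensive improvement to reporting and interpretation, not a flaw that invalidates the audit.

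**What to change.** In 4.6 and 8:
- Report Phase 1 management, discharge and referral results separately for 2019, 2020 and 2021.
- Keep the full 36-month before/during comparison.
- Add, as a sensitivity analysis, a contrast restricted to records dated before Phase 2 briefings or posters began (2019 v 2020, ending earlier if they began in late 2020).
- Record the date on which briefings and posters started.
- State that 2021 is to be interpreted as pandemic plus study activity, and name the overlap as a limitation.

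**Cost.** Only wording and analysis change, and no further data are needed. The restricted contrast has fewer pandemic months and less precision. With equal monthly case numbers and similar proportions, its standard error grows by a factor of √[(1/12 + 1/12)/(1/12 + 1/24)] = 1.15 when the pandemic side starts in January 2020. With an assumed March 2020 start, comparing 14 months with 10 in place of 14 with 22, the factor is √[(1/14 + 1/10)/(1/14 + 1/22)] = 1.21. This loss applies to the sensitivity contrast alone, because the full-period result is still reported.

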5.2 Eligibility Criteria

5.2.1 Inclusion Criteria

Phase 1 medical record audit: All patients (up to 30 years of age) presenting to ED at RNSH from 1st January 2019 - 31st December 2021 (36 months) will be reviewed for evidence of head injuries.

Phase 2 telephone interview: Patients (up to 30 years of age) who present to ED with a head injury will be included in the study and who are discharged home or admitted to the ward.

5.2.2 Exclusion Criteria

Phase 2: Patients older than 31 years, patients given a triage category 1, and patients allocated to the resuscitation area, children identified as a child at risk at time of treatment or children transferred to a tertiary paediatric hospital.

6. Informed Consent Process

Phase 1 medical record audit: For the collection of retrospective data we would request a waiver of consent given the difficulties of obtaining consent for this patient cohort. There would be no phone calls to this group of patients.

Waiver of consent;

- a) *The benefits from the research justify any risks of harm associated with not seeking consent:* There are significant potential benefits of the research in providing information on which to enhance the current approaches to treatment of people presenting to mental health inpatient units. The outcomes of this research have the potential for significant impact on inpatient mental health services.
- b) *It is impracticable to obtain consent:* We estimate that there will be up to 267,000 medical records reviewed. These are retrospective audits from a time period of up to 36 months ago. Therefore it would not be feasible to contact that number of potential participants for consent within the resources of this study.

- c) *There is no known or likely reason for thinking that participants would not have consented if they had been asked:* There is no known reason for participants in the program to not consent for de-identified data to be analysed in the way proposed.
- d) *There is sufficient protection of their privacy:* Audit data will be de-identified at the point of data collection. No quotations or other textual data will be retained from the audit and data will be aggregated for reporting.
- e) *There is an adequate plan to protect the confidentiality of data:* Data analysed and stored for the study will be stored securely, will contain no identifying information, and will be reported only in aggregated and summarised form.
- f) *In case the results have significance for the participants' welfare there is, where practicable, a plan for making information arising from the research available to them:* Stored data will not contain identifying information and will be aggregated for reporting. Data are retrospective. Findings will inform emergency management of patients presenting with head injury and may therefore benefit future consumers.
- g) *The possibility of commercial exploitation of derivatives of the data or tissue will not deprive the participants of any financial benefits to which they would be entitled:* There is no foreseeable commercial application for the findings of this study.
- h) *The waiver is not prohibited by State, federal, or international law:* Audit data will be de-identified on collection. Data that are de-identified are not subject to the statutory guidelines on research in New South Wales under the Health Records and Information Privacy Act 2002 (Information and Privacy Commission New South Wales, 2004). Use of administrative data for a secondary purpose is addressed in the Privacy Act 1988 (Cth), sections 16B and 95A.

Phase 2 telephone interview: potential participants will be identified by clinicians or the emergency research volunteers, who will seek their permission to participate in telephone interviews whilst the patient is in the ED using the participant information sheet and consent form. Verbal consent will be obtained prior to commencement of the telephone interview and documented.

Within all ED clinical areas there will be available study information sheets that align with the posters if any potential participants request further information about the study. At the start of the telephone interview the study information will again be provided as part of the telephone script and verbal consent obtained, documented and dated. If a potential participant declines while in the ED the treating clinician will complete the withdrawal form for the study. No impact on care practices will occur because of withdrawal. Clinicians will be mindful and respectful of patients/parents/carers decline or choose to withdraw from the study.

6.1 Participant Withdrawal

All patients/parents/carers will have the opportunity to withdraw/opt out at any stage of the study. Including those who may choose to decline during their initial presentation to ED. In this instance the patient/parent/carer will complete a form withdrawing consent from the study this will be deposited into a sealed collection box (in paediatric area or fast track area) and will be collected by the lead researcher.

7. ADVERSE EVENT REPORTING

This is a low risk project for patients/parents/carers. We do not anticipate the procedures used in this study will cause concern or harm for participants. However, we will implement measures to mitigate any potential distress. If the patient (or their person responsible) becomes distressed during the telephone interview, he or she will be referred to the ED social worker or other appropriate helpline agency/ services. If patients reported ongoing symptoms or concerns they would be encouraged to seek further medical attention through their general practitioner or present to their local ED.

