2.2 Research Question

Phase 1: Primary question: What are the characteristics, patterns and outcomes of people (up to 30 years of age) that present with signs and symptoms of head injuries to one major tertiary referral hospital ED and does the COVID-19 pandemic and social isolation impact on or change the presentation rate for patients with head injuries?

Phase 2: To follow up on a patient's health trajectory journey at 10-14 days and then four weeks post discharge. Follow up will involve exploring the discharge processes, patient symptoms/progress, community management and follow up with a community practitioner.

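### Advice given at the 10-14 day call may prompt some of the GP and ED contact reported at four weeks, and the protocol does not separate prompted from usual care

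*Protocol*

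**What the plan says.** Section 5.1 of the protocol schedules two telephone interviews with the same participants, "who will be contacted 10-14 days post injury and then four weeks post discharge". Section 2.2 gives one description of content for both time points: "Follow up will involve exploring the discharge processes, patient symptoms/progress, community management and follow up with a community practitioner". Section 5.1 adds that the interview collects "feedback on the discharge process, ongoing symptoms, return to sport, school, study or work or the need for further medical review".

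The second of the secondary objectives in section 3 is "How are head injury patients managed in the community and the need for further management", and section 4.6 repeats this under the primary outcome.

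Section 7 sets out what happens at an interview: "If patients reported ongoing symptoms or concerns", then "they would be encouraged to seek further medical attention through their general practitioner or present to their local ED". It does not limit this to one of the two calls, so it applies at 10-14 days as well as at four weeks.

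Section 8 describes Phase 2 as semi-structured interviews analysed thematically. Its list of Phase 2 data names neither the advice given by the interviewer nor the dates of later health-care contacts.

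**The concern.** The behaviour that the first call may encourage, seeing a GP or attending an ED, is among the behaviours that the second call asks about. A patient who sees a GP between the calls may have gone as part of ordinary community management, or because the interviewer suggested it. At four weeks the two look the same unless someone recorded the advice and the timing.

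The route is selective. Advice goes only to patients with ongoing symptoms or concerns, the group whose management after discharge matters most to Phase 2. Encouragement would be expected to raise contact, so any distortion would make four-week follow-up look more complete than usual practice. Section 11 expects the results to lead to policy change and to identify gaps in community care, so it matters that four-week contact is labelled correctly.

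**Working it through.** **The plan's own figure.** The synopsis takes 350 eligible Phase 2 patients and 80% participation: 350 × 0.80 = 280. This reproduces. The synopsis also gives 150 as the planned Phase 2 size. That is a separate inconsistency and does not bear on the mechanism. The counts below use 280, as in sections 4.3 and 8.1.

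**The mechanism, link by link.**

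1. The same people are called twice (sections 2.2 and 5.1).
2. At either call, reported symptoms or concerns lead to encouragement to seek care (section 7). Only encouragement at the first call can affect contact reported at the second.
3. Community management and follow-up with a community practitioner are explored at both calls (section 2.2), and community management is listed under the primary outcome (section 4.6).
4. Sections 2.2, 4.6, 5.1, 7 and 8 to 8.2 contain no step that records the advice, dates contacts against the first call, or separates prompted from unprompted care.

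**The exposed window.** For a patient discharged on the day of injury, the time between the calls is 28 − 14 = 14 to 28 − 10 = 18 days. At least half of the four-week period therefore falls after the first call.

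**What is and is not exposed.**

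| Item | Affected by this route? |
|---|---|
| Contact reported at the first call | No; it precedes any interview prompt |
| Need for further management or review | No; encouragement can change attendance, not need |
| GP, ED or practitioner contact between the calls | Yes |

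**Size.** The protocol gives no symptom or uptake rate, so every rate here is an assumption. Let

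- s = share symptomatic at the first call, 10-40%;
- u = share of those not already seeking care, 50-80%;
- q = share of those who attend only because of the prompt, 10-50%.

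Added contact at four weeks = s × u × q.

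| Case | s × u × q | Percentage points | Of 280 |
|---|---|---|---|
| Low | 0.10 × 0.50 × 0.10 = 0.005 | 0.5 | 1.4 |
| Middle | 0.20 × 0.80 × 0.30 = 0.048 | 4.8 | 13.4 |
| High | 0.40 × 0.80 × 0.50 = 0.160 | 16.0 | 44.8 |

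**The case against.** The strongest reply has four parts.

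*Phase 2 is qualitative.* The protocol defines no four-week care proportion and plans no comparison of the two calls. In a semi-structured interview a patient can say that a visit followed the study call, and this can be coded. That stands in part: the percentage points above illustrate a possible distortion and do not measure an error in a planned estimate. But a theme about patients seeking GP review is exposed in the same way as a count, and relying on patients to volunteer the reason is weaker than asking.

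*The first call already captures unprompted care.* This stands. A reader might infer that the advice would hide the gaps in community care the study is looking for. The documents do not support that: a patient still symptomatic at 10-14 days with no follow-up would be seen at the first call.

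*The forms are not shown.* The telephone script and interview forms mentioned in sections 6 and 9 may already log advice or dates, and the data list in section 8 need not be exhaustive. This stands as a caution; the protocol does not require either item. Nor could a later analysis plan repair the gap, because information not collected at the calls may not be recoverable.

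*The advice is a safety measure.* Agreed. The point concerns measurement and reporting only.

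Two other strong readings also fail. One multiplies the share symptomatic by the share who act on the advice and calls the whole product study-induced; for instance, 0.30 × 0.50 = 0.15, or 42 of 280. That counts patients who had already sought care or would have done so anyway. The other treats the need for further management as distorted, although encouragement does not create need.

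**Conclusion.** The point holds as a measurement weakness that is cheap to correct. GP and ED contact reported at four weeks may mix usual community management with visits prompted by the 10-14 day call, and the protocol as written gives no means of telling them apart. The expected direction is towards more contact than usual practice would show.

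The size is unknown. On the assumed rates it is about 0.5 to 16 percentage points, or about 1 to 45 of 280, with a middle case of 4.8 points (about 13). The existence of the route does not depend on these rates, but whether it matters in practice does. It does not call the first-call data, the stated need for further care or the feasibility of Phase 2 into question.

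**What to change.** Leave the advice in section 7 unchanged and keep the four-week outcome.

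- **First-call form:** record GP, ED and other health-care contacts since discharge, with dates, and whether the interviewer advised seeking care.
- **Second-call form:** date each contact since the first call and ask whether it followed the study call.
- **Reporting:** give contact before the first call as the unprompted measure, alongside the four-week result. Show contact after the first call by whether advice was given, as description only: advice is confounded with symptoms, so the difference between these groups is not the effect of the prompt.
- **Limitation:** state that four-week care may include visits prompted by the call.

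Redefining the outcome in section 4.6 as contact before the first call only is not recommended, because it would narrow an objective that runs to four weeks.

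The cost is a few extra interview items and a sentence in the protocol. The remaining weakness is that the unprompted measure covers only the first 10-14 days.
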